Dental anxiety is linked to avoidance behavior and an increased pain response during dental procedures.^{1,2} At this time, limited methods for non-pharmacological anxiety control exist. The burden of sedation dentistry comes with many risks and financial costs. Some serious unwanted side effects include compromise to the patient's respiratory drive, airway reflexes and airway patency, as well as the cardiovascular system.³ Sedation for anxiety control is also costly for the patient and healthcare system, with deleterious effects on access to care. **Dentistry is in need of anxiety control measures other than pharmacological sedation** to reduce the risk to patients, lower the cost of treatment and thus increase access to dental care. One promising approach is animal-assisted therapy (AAT) using a well-trained therapy dog. In medical settings, AAT has been implemented in various clinical situations and has been shown to help reduce pain and stress indicators in patients.⁴ Research into AAT as a non-pharmacological behavior management and anxiety reduction techniques in dentistry is limited as many publications are surveys⁵ with a low sample size and are not conducted in the pediatric and/or dental patient population.²

To explore the effectiveness of non-pharmacological anxiety-reduction approaches, we will study the effects of animal-assisted therapy (AAT) on pediatric patients undergoing invasive dental procedures that include an injection. The University of North Carolina has a unique opportunity to explore animal-assisted therapy because the dental school has a certified therapy dog. Our central hypothesis is that children who interact with a therapy dog before their dental procedure will have significantly lower physiologic and subjective responses to stress. We will test this hypothesis by following aims:

Primary Aim: We will measure the effects of animal assisted therapy on pediatric patients' stress levels by analyzing objective physiologic measures (salivary amylase and cortisol) during invasive dental procedures.

Supplemental Aims: We will measure participants' heart rate throughout dental visit, will evaluate patients' perceptions of pain and anxiety using pre-, intra-, and post-procedural surveys to assess the patients' subjective responses to animal-assisted therapy and will analyze participants' behaviors using observational coding.

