Figure 1: Overall Trial Design. Subject participation commences with consent and a pre-procedural survey. Subjects are randomized to a dog intervention or a control intervention (coloring or sitting in silence). The first baseline saliva sample S1 is collected, followed by the 2-minute therapy dog interaction for experimental participants (controls will sit in the room coloring for 2 minutes without a dog or sit in the room in silence). A second saliva sample S2 is collected 8 minutes later, after the intervention. The local anesthetic injection or insertion of handpiece will occur, followed by the third salivary sample S3 collected 8 minutes later to ensure sufficient time for variation in salivary biometrics. The dental procedure will continue and at the end of the visit participants will provide their last saliva sample S4 and fill out a post-procedure survey about their experience, perceived pain, anxiety and future expectations. Study participation concludes. Video (GoPro), skin galvanic response and heart rate data are continuously collected throughout the procedure. Salivary samples are processed for alpha-amylase and cortisol by the UNC Biobehavioral Lab (BBL).

Primary Aim: We will measure the physiologic effects of animal assisted therapy on pediatric patients' stress levels. Salivary alpha-amylase (sAA) functions as a digestive enzyme involved in the breakdown of glycogen and starch as well as part of the immune system by protecting the oral cavity from harmful microorganisms.³⁰ Salivary alpha-amylase increases in response to stress.³¹ In a study of 99 patients undergoing an invasive dental procedure, Jafari et. al presented evidence to support the dependability and objectivity of using sAA to measure the acute stress response in patients with dental anxiety.³²

Another physiological indicator of stress response that can be measured in the dental setting is salivary cortisol. The hypothalamic-pituitary-adrenal axis (HPA) is an important aspect of the endocrine system which leads to release of cortisol from the adrenal glands when the body is subject to physical or emotional stress.³³ As supported by the 2007 meta-analysis by Miller et. al exploring cortisol levels and stress, the use of salivary cortisol levels is well cited in the scientific literature to be a validated biomarker for stress.³⁴

To collect a saliva sample, the research team places a salivette in the mandibular vestibule for 5 minutes at the following timepoints:

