Table 2: Timepoints for salivary data collection

Timepoint	Description
S1	Baseline (pre-intervention, in consultation room)
S2	Post-intervention (8 minutes after intervention)
S3	8 minutes into the dental procedure
S4	8 minutes after completion of the procedure at the end of the study visit

Supplemental Aims: We will measure participants' heart rate throughout dental visit, will evaluate patients' perceptions of pain and anxiety using pre-, intra-, and post-procedural surveys and will analyze participants' behaviors using observational coding.

The Shimmer 3 GSR+ and Polar are small wearable wrist devices that measure heart rate through the wrist, with Shimmer 3 GSR+ also measuring sweat response through sensors that are fastened to the fingers. The Shimmer/Polar device will be connected to the patient during the pre-procedural interview, dog or control intervention, and procedure, continuously collecting heart rate and/or galvanic skin response (GSR) data.

Because heart rate is known to reliably increase under acute mental stress, it is widely used in medical research to evaluate stress response.³⁵ The Galvanic Skin Response (GSR) is a biomarker that quantifies the small electrical current induced by sweat which is released when the body is under stress.³⁶ The most significant psycho-activity and concentration of the epidermal sweat glands is on the sole of foot and the palm of the hand, particularly on the volar surface of the finger tips.³⁶ In a study completed by Caprara et. al in 2003, GSR was linked to increased dental anxiety in patients before undergoing a root canal treatment.³⁷

The video of the procedure as well as the heart rate data and GSR from the Shimmer device is loaded on to an external hard drive. The video will be coded with established behavioral codes using the Noldus software. The HR and GSR data are reviewed for inconsistencies using MindWare software. Both software are on a computer located in the bio-behavioral lab (BBL). The salivettes are transferred in a temperature-controlled container to the BBL where they are analyzed by ELISA for salivary alpha-amylase and salivary cortisol.

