Pre-intervention and post-intervention interviews will include the Child Fear Survey Schedule-Subset Dental (CFSS-SD), and the Modified Child Dental Anxiety Scale (MCDAS) to rate anxiety. To rate pain, the Wong-Baker FACES Scale (WBS), a numeric scale, and Visual Analog Scale (VAS) will also be used. The three pain rating scales will be repeated immediately after the injection. At the end of the procedures, the research team will repeat the CFSS-SD and the MCDAS for anxiety. They will also ask the child to rate his or her pain level again using the WBS, numeric scale, and VAS.

Pictorial representation of pain response, like The Wong-Baker FACES Scale (WBS), are preferred by children to express their level of pain regardless of age.³⁸ The Modified Child Dental Anxiety Survey (MCDAS) and the Children's Fear Survey Schedule, Dental Subset (CFSS-SD) are valid and reliable questionnaires in rating a child's anxiety in the dental setting.³⁹

STATISTICAL ANALYSIS PLAN:

To evaluate the values obtained on the various surveys, a RH Row Mean test will be utilized to compare questions that have Likert scale / ordinal responses and a chi square test will be used for categorical data. A bivariate analysis will be performed to compare the treatment outcome relative to the main exposure, which is the presence of the animal assisted therapy. The significance level will be $P < 0.05$.

Bibliography

1. Lima, D. S. M. *et al.* Does previous dental care experience make the child less anxious? An evaluation of anxiety and fear of pain. *Eur. Arch. Paediatr. Dent.* **22**, 139–143 (2021).
3. Coté, C. J. & Wilson, S. Guidelines for monitoring and management of pediatric patients before, during, and after sedation for diagnostic and therapeutic procedures. *Pediatr. Dent.* **41**, 259–260 (2019).
4. Marcus, D. A. *et al.* Animal-assisted therapy at an outpatient pain management clinic. *Pain Med.* **13**, 45–57 (2012).

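### No analysis is written for the primary salivary assays; the one rule that could cover them leaves the outcome undefined and has no place for S1 as a covariate

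*Combined protocol and SAP*

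**What the plan says.** The Primary Aim under Specific Aims is to study stress by "analyzing objective physiologic measures (salivary amylase and cortisol) during invasive dental procedures". Table 2 sets four saliva samples per child. S1 is labelled "Baseline (pre-intervention, in consultation room", S2 follows the intervention, S3 is taken at "8 minutes into the dental procedure", and S4 comes after the procedure ends.

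The Statistical Analysis Plan is one paragraph. It opens with the surveys: "a RH Row Mean test will be utilized to compare questions that have Likert scale / ordinal responses", with a chi-square test for categorical data. It then gives the general rule, "A bivariate analysis will be performed to compare the treatment outcome relative to the main exposure, which is the presence of the animal assisted therapy", and a significance level of 0.05. It mentions no assay, saliva sample, summary measure, scale or covariate.

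On the order of events, the Figure 1 caption says "Subjects are randomized to a dog intervention or a control intervention (coloring or sitting in silence" and only then "The first baseline saliva sample S1 is collected, followed by the 2-minute therapy dog interaction for experimental participants". The design section adds that each child is assigned at enrollment to a random weekday, which fixes whether the dog is available. S1 therefore precedes the intervention but follows assignment.

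**The concern.** The primary aim rests on two assays measured four times, yet no analysis is written for them. If the bivariate rule is meant to apply, two things follow.

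- **Precision.** Each child supplies a baseline value that is usually informative about the later ones. A comparison of one outcome with one exposure cannot adjust for it. The documents state no sample size, so there is no ground for assuming that precision is plentiful.
- **Choice.** With assay, sample and summary all open, the result that decides the primary aim could be picked after the data are seen.

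**Working it through.** **Inputs.** From the documents: two biomarkers; one baseline and three later samples; significance level 0.05. Not in the documents: the correlation r between S1 and a later sample, any SD, any sample size. I assume r from 0.2 to 0.7 and independent children. The plan has no figure of its own to reproduce.

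**Step 1: one later sample.** Let the S1 variance be 1 and the later-sample variance s². Large-sample variance per child:

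- later sample only: s²
- change from S1: s² + 1 − 2rs
- adjusted for S1: s²(1 − r²)

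Extra children that adjustment is worth = variance ratio − 1.

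Against the later sample only, s cancels and the gain is 1/(1 − r²) − 1:

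- r = 0.2: 1/0.96 − 1 = 4%
- r = 0.3: 1/0.91 − 1 = 10%
- r = 0.5: 1/0.75 − 1 = 33%
- r = 0.7: 1/0.51 − 1 = 96%

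Against a change score, the variance difference is (1 − rs)², which is never negative:

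| r | s = 1 | s = 1.5 |
|---|---|---|
| 0.3 | 1.40/0.91: 54% | 2.35/2.0475: 15% |
| 0.5 | 1.00/0.75: 33% | 1.75/1.6875: 4% |
| 0.7 | 0.60/0.51: 18% | 1.15/1.1475: 0.2% |

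**Step 2: small samples.** Fitting one covariate multiplies the variance by about (N − 3)/(N − 4), with N the total number of children. Adjustment then beats the later sample alone only if r exceeds 1/√(N − 3): 0.24 at N = 20, 0.16 at N = 40, 0.10 at N = 100.

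**Step 3: mean of S2 to S4, unit variances.**

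- Equal correlation r between all samples: unadjusted (1 + 2r)/3, adjusted (1 + 2r)/3 − r². At r = 0.3, 0.5 and 0.7: 0.533/0.443, 0.667/0.417 and 0.800/0.310, so gains of 20%, 60% and 158%.
- Correlation decaying by sample (r, r², r³ from S1): unadjusted (3 + 4r + 2r²)/9; adjusted subtracts [(r + r² + r³)/3]². At the same r: 0.487/0.467, 0.611/0.526 and 0.753/0.492, so gains of 4%, 16% and 53%.

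**Step 4: open choice of outcome.** With no true effect, the chance that at least one test is significant at 0.05 is:

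- two independent biomarkers at S3 only: 1 − 0.95² = 9.75%, about 10%
- two biomarkers by three later samples, six independent tests: 1 − 0.95⁶ = 26%
- six tests, simulated with correlations of 0.3 to 0.9 between samples of the same biomarker: about 25% down to 16%

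**Step 5: risk in using S1.** If knowing the arm shifted S1 by d, the adjusted estimate would move by −r·d (equal variances) and a change score by −d. For an assumed d of 0.1 SD, the adjusted estimate moves by 0.03, 0.05 or 0.07 SD at r = 0.3, 0.5 or 0.7. The change score moves by 0.10 SD and the later sample alone does not move.

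**The case against.** **The plan may say nothing about saliva, rather than choose badly.** The paragraph opens on surveys and never mentions an assay. A reader might infer that the sponsor deliberately chose an unadjusted test that discards S1. The text does not support that: the rule reaches saliva only by elimination, and an outcome defined as change from S1 would still be bivariate. What stands is an omission, plus a fallback rule that cannot carry a covariate.

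**The outcome is not wholly open.** The aims name both biomarkers, and the aim's reference to the procedure itself can be read as pointing to S3, the only sample taken during it. A reader might infer that six tests, and hence 26%, is this trial's error rate. It is only the upper reading; two tests and about 10% is the lower. No document says that results will be picked.

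**The gain is uncertain.** This is right. The 158% figure needs equal correlations on both sides of an injection and an outcome that no document names. The change-score gain nearly vanishes if later values are more variable. Assignment by weekday could make children seen on the same date alike. That could raise or lower the gain over the later sample alone, depending on whether the date effect also acts on S1.

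**S1 follows assignment.** This also stands. Adjustment is a trade-off, though the possible shift is smaller than with a change score.

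**Conclusion.** The concern holds in a limited form. The SAP specifies no analysis for the primary assays, and the one rule that could apply leaves the outcome undefined and cannot adjust for S1. That much is clear from the text.

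The size of the gain is not. Under equal or unequal variances, adjustment has large-sample variance no higher than either the later sample alone or a change score. For one later sample it is worth 4% to 96% more children than the later sample alone, over assumed correlations of 0.2 to 0.7. Against a change score it is worth between 0.2% and 54%, over correlations of 0.3 to 0.7 and the two SD ratios shown. All these figures treat children as independent; no figure is claimed for data clustered by date. The case for fixing one outcome in advance does not depend on the S1 correlation.

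**What to change.** Replace the bivariate rule, for saliva only, with one primary analysis fixed before the data are examined:

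- One named biomarker at one named later sample (or one named summary), on a scale set in advance, for example log for both S1 and the later value.
- A linear model on arm and S1, with standard errors that allow for visit date because assignment is by weekday.
- The arm effect reported with a 95% CI; the other biomarker and samples labelled secondary.
- The same comparison without S1 as a sensitivity analysis, because S1 follows assignment.

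If S3 is named, its timing must first be reconciled. The Figure 1 caption places the injection or handpiece insertion first, "followed by the third salivary sample S3 collected 8 minutes later to ensure sufficient time for variation in salivary biometrics", whereas Table 2 has it at "8 minutes into the dental procedure".

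The cost is SAP wording and routine analysis; S1 to S4 are already planned. The downside is the possible shift in S1 described above, which the sensitivity analysis is there to expose.

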TITLE: Evaluating effects of animal assisted therapy on anxious pediatric dental patients using objective physiologic measures and self-reports of stress

NCT NUMBER: NCT04708028

DOCUMENT DATE: March 20, 2024

TITLE: Evaluating effects of animal assisted therapy on anxious pediatric dental patients using objective physiologic measures and self-reports of stress

ABSTRACT:

A striking 50-80% of adults and 6-22% of children suffer from dental anxiety which leads to disruptive behavior during appointments and avoidance of regular dental care. Though routinely used, common pharmacological interventions (i.e. oral sedation, general anesthesia) for anxiety management carry risks of adverse effects including stress on the respiratory and cardiovascular systems, neurologic injury, and even death. Data from various healthcare settings show reductions in pain and stress indicators in patients after implementation of a therapy dog for appointments. However, few studies have explored the physiologic and subjective effects of AAT on pediatric dental patients undergoing invasive procedures. To address this gap in knowledge and explore the effectiveness of animal-assisted therapy (AAT) in pediatric dentistry, we will study the subjective and objective responses of patients undergoing operative dental procedures that include an injection.

Our central hypothesis is that children who interact with a therapy dog before their dental procedure will have significantly lower physiologic and subjective, self-reported responses to anxiety. We will test this hypothesis with the following aims: **We will measure the physiologic effects of animal assisted therapy on pediatric patients' stress levels** by analyzing salivary stress hormones (i.e. alpha-amylase and cortisol) during invasive dental procedures (primary aim). For supplemental aims, **we will measure participants' heart rate throughout the dental visit, will evaluate the patients' self-perceptions of pain and anxiety** using pre-, intra- and post-procedural validated scales to assess responses to AAT and **will analyze participants' behaviors using observational coding.** Data will guide the implementation of AAT as a non-pharmacological anxiety management tool in dentistry, with the goal of improving access to care and patient safety among anxious pediatric patients.

SPECIFIC AIMS:

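### The primary aim has two salivary markers with three post-baseline samples each, but no deciding endpoint, success rule or multiplicity control; if either marker suffices, two-sided error is about 7-10%, not 5%.

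*Combined protocol and SAP*

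**What the plan says.** The Specific Aims state the primary aim as the effect of therapy on stress, assessed by "analyzing objective physiologic measures (salivary amylase and cortisol) during invasive dental procedures". The Abstract names the same two markers. Neither place ranks them. The hypothesis is directional: the Abstract expects "significantly lower physiologic and subjective, self-reported responses to anxiety" in children who meet the dog.

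Table 2 lists four saliva samples: S1 at baseline, S2 after the intervention, S3 within the procedure and S4 after it. The Figure 1 legend confirms that "Salivary samples are processed for alpha-amylase and cortisol", so each marker has three post-baseline values.

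The Statistical Analysis Plan is three sentences long:

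- The first names tests for questionnaires and categorical data: "To evaluate the values obtained on the various surveys, a RH Row Mean test will be utilized" for ordinal items, and chi-square for categorical data.
- The second reads "A bivariate analysis will be performed to compare the treatment outcome relative to the main exposure", the exposure being the presence of the therapy. The outcome is not identified.
- The third sets the level: "The significance level will be" P < 0.05.

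No saliva test is named. That the second sentence is meant to cover saliva is an inference, but no other sentence could.

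**The concern.** A primary conclusion has a defined error rate only if the plan says in advance which result decides it. Here the marker, the timepoint (or summary over timepoints) and the success rule are all open. The plan sets neither a minimum nor a maximum number of primary-aim tests, and each may be run at an unadjusted 0.05.

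As written, all three choices can be made after results by group are known. A significant amylase result at S2 and a significant cortisol result at S4 could equally be reported as meeting the primary aim. Whether the error exceeds 5% depends on a rule the plan does not give: it does if either marker is enough, and it does not if both are needed on one comparison each. The Abstract says the data will guide use of the therapy, so a positive primary result would be treated as confirmatory. Supplemental outcomes are labelled as such and are not counted here.

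**Working it through.** **Inputs.** From the documents: two primary markers (Abstract, Specific Aims), three post-baseline samples each (Table 2), significance level 0.05 (Statistical Analysis Plan). Assumed, because the documents are silent: two-sided tests, and a correlation r between the two markers' test statistics of 0 to 0.9. There is no sample size or power figure to reproduce; the 0.05 is an input.

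**1. One test per marker, both null hypotheses true.** Let Z1 and Z2 be standard bivariate normal with correlation r, and c = 1.960.

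- Either marker significant: 1 − P(|Z1| < c, |Z2| < c). At r = 0 this is 1 − 0.95² = 9.75%.
- Either marker significant in the lower direction: 1 − P(Z1 > −c, Z2 > −c). At r = 0 this is 1 − 0.975² = 4.94%.
- Both markers significant: 0.05 + 0.05 − P(either). At r = 0 this is 0.10 − 0.0975 = 0.25%.

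| r | Either, two-sided | Either, lower | Both, two-sided |
|---|---|---|---|
| 0 | 9.75% | 4.94% | 0.25% |
| 0.2 | 9.64% | 4.84% | 0.36% |
| 0.4 | 9.32% | 4.66% | 0.68% |
| 0.53 | 8.99% | 4.49% | 1.01% |
| 0.7 | 8.35% | 4.17% | 1.65% |
| 0.9 | 7.04% | 3.52% | 2.96% |

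A single two-sided 0.05 test errs in the lower direction 2.5% of the time, so the either-marker rule multiplies that by 3.52/2.5 = 1.4 to 4.94/2.5 = 2.0.

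**2. Timepoints also open (illustration; the plan does not prescribe it).** Six marker-by-timepoint tests, any |Z| > 1.960 counting. Independent tests give 1 − 0.95⁶ = 26.5%. Simulation with 1,000,000 multivariate-normal draws per setting gives:

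| Correlation within marker | Correlation between markers | Any of six |
|---|---|---|
| 0.3 | 0 | 25.4% |
| 0.7 | 0.4 | 19.4% |
| 0.9 | 0.4 | 15.2% |
| 0.9 | 0.9 | 10.8% |

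**3. With Holm across the two markers.** The first step tests each at 0.025, c = 2.241.

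- Two-sided: 1 − 0.975² = 4.94% (r = 0), 4.76% (0.4), 3.62% (0.9).
- Lower direction: 2.48%, 2.38%, 1.81%.

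**4. Power, from assumed starting values.**

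- Holm's first step: Φ(1.960 + 0.842 − 2.241) = 71.2% from 80%; Φ(1.960 + 1.282 − 2.241) = 84.1% from 90%.
- Both markers required: from 80% each, 0.8² = 64.0% (r = 0), 67.6% (0.4), 75.0% (0.9); from 90% each, 0.9² = 81.0%, 82.7%, 86.9%.

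**The case against.** The strongest reply is that 7-10% belongs to a rule the plan never states. The aim joins the markers with a plain conjunction; read as requiring both, one comparison each, the error cannot exceed 5%. The hypothesis is also directional, and the rate of false claims of benefit stays below 5% even under the either-marker rule. Both points are right as arithmetic. They make the 7-10% conditional and show why the lower-direction rate belongs beside it. They do not supply the missing rule: the conjunction describes what is measured, not what must be significant, and 3.5-4.9% is still above the 2.5% of a single two-sided test.

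A second reply is that the plan hints at S3. The aim concerns stress during procedures, and the Figure 1 legend describes the injection or handpiece insertion as "followed by the third salivary sample S3 collected 8 minutes later to ensure sufficient time for variation in salivary biometrics". This supports S3 as a candidate but does not designate it.

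A third reply is that colouring and silent controls leave the comparison itself open, so that fixing the markers is not enough. Figure 1 sets the dog intervention against control, and the Statistical Analysis Plan defines exposure as presence of the therapy, so the primary comparison can be read as dog versus control. Assignment by weekday is a real issue but a separate one; the figures here take each test as valid at its nominal level.

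Finally, an open choice is an opportunity. Nothing in the documents shows that anyone has selected results after seeing them.

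**Conclusion.** The concern holds. No section names a deciding marker, timepoint or summary, a success rule, sidedness or a multiplicity method for the primary aim, so the error rate of its conclusion is undefined. That finding rests on the text and needs no assumed correlation.

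The size is conditional on two-sided tests, one comparison per marker, either marker sufficing and r between 0 and 0.9: about 7-10% overall and 3.5-4.9% for a false claim of lower stress. The 7-10% leaves out the choice among timepoints. If that is open too, the illustration gives about 15-26% with between-marker correlation up to 0.4, falling to about 11% if all correlations are 0.9. This should be corrected; it bears on how the main claim can be read and is cheap to put right.

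**What to change.** Before outcome data are examined by group, amend the Statistical Analysis Plan as follows.

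1. **One endpoint per marker, adjusted for S1.** For example, the dog-versus-control difference at S3 from a linear model with S1 as covariate. S3 is the only sample Table 2 places within the procedure, which fits the aim; the sponsor may justify another timepoint or a summary over samples. Any transformation should be fixed in advance.
2. **Clarify S3 timing if S3 is used.** The Figure 1 legend counts 8 minutes from injection or handpiece insertion, and Table 2 counts 8 minutes into the procedure. These agree only if that event marks the start of the procedure.
3. **One success rule.** Either (a) either marker suffices, with Holm or a pre-stated fixed sequence at two-sided 0.05, the sponsor fixing any marker order; or (b) both markers are required, each at two-sided 0.05.
4. **Everything else.** Report the remaining saliva timepoints and all supplemental outcomes with 95% confidence intervals and no confirmatory claims.

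The change is wording plus one timing clarification, since S1 and S3 are already collected. The price is power, shown from assumed values because the plan states none. Holm's first step takes 80% per marker to about 71% and 90% to about 84%. Requiring both gives joint power of 64-75% from 80% each, or 81-87% from 90% each. A fixed sequence costs the first marker nothing, but the second can be claimed only if the first is significant.
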